10. Inability, in the opinion of the investigator or clinic coordinator, to coordinate use of a metered dose inhaler (MDI).
11. Changes of ischemic heart disease or arrhythmia on screening ECG (not excluded for occasional, $\leq 3/\text{min}$, atrial or ventricular premature contractions, or clinically insignificant sinus bradycardia).
12. Pregnancy. If potentially able to bear children, not using an acceptable form of birth control (see ACRN MOP, Appendix One).

13. Inability, as evidenced through biological quality control testing, to correctly use an AirWatch™ device for recording peak flow measurements.

C. Inclusion Criteria For Randomization (at Visit 4)

1. Prebronchodilator FEV₁ • 80% of predicted.
2. If FEV₁ is > 80% predicted, average variability $\frac{PM - AM}{1/2 (PM+AM)}$ in PEF > 20% during the final two weeks of the run-in period (weeks 5 and 6).
3. Ability of the subject to measure his/her AM and PM PEF on schedule using the AirWatch device, to appropriately mark the measurements using the post-medication marker, and to accurately transcribe the PEF measurements onto his/her diary cards at least 85% of the time during the last two weeks of the run-in.

D. Exclusion Criteria For Randomization (at Visit 4)

1. Significant exacerbation of asthma during the run-in period (see section VI for definition of significant exacerbation and guidelines for treatment).
2. Inability to comply with regular use of MDI (use of scheduled MDI less than twice/day on more than 12 days in the run-in period), as reflected by the diary card.
3. Failure to record peak flow measurements and symptoms in a symptom diary on average more than two days/week during the run-in period.
4. Any changes with regard to any of the exclusion criteria identified for visit 1 (see Section IIIB above).
5. Use of an average of • 16 puffs of albuterol per 24 hours during last week of run-in (week 6).
6. Prebronchodilator FEV₁ < 55% of predicted normal.

E. Criteria for Stratification into Two Subgroups (based on severity of airway obstruction and/or PEF stability) (Subgroups I and II) at Visit 5

Criteria for stratification into *Subgroup I*:

1. FEV₁ is > 80% predicted and PEF variability $\frac{PM - AM}{1/2(PM+AM)}$ in previous two weeks is ≤ 20%.

Criteria for stratification into **Subgroup II**:

1. $FEV_1 \leq 80\%$ of predicted.
2. If FEV_1 is $> 80\%$ predicted, average variability $\frac{PM-AM}{1/2(PM+AM)}$ in PEF $> 20\%$ during the previous two weeks.

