2. If patients meet criteria for treatment failure status, their dose of inhaled corticosteroids will be increased to the dose they were receiving at visit 4 (800 $\mu\text{g}/\text{day}$) delivered by an open-label inhaler. Study inhalers of corticosteroids (or its placebo) will be returned to the clinical center. If they meet the criteria detailed in Section VI, they will be treated with appropriate rescue algorithms for an asthma exacerbation. Study inhalers of salmeterol (or placebo) will be continued unless the physician can document that treatment failure status was causally related to taking this medication. They will continue to participate in the study until its termination (intent-to-treat analysis), but no further reductions in inhaled corticosteroid dose will be attempted during this time period. For safety reasons, all subjects will be seen within one week ($\pm 3\text{d}$) from the day they were categorized as achieving treatment failure status. Following this "safety" visit, subsequent protocol visits will continue in accordance with the visit schedule established at Visit 1 (see SOCS/SLIC MOP for details concerning possible replacement of scheduled protocol visits with treatment failure related visits).

IV. OUTCOME VARIABLES

The primary outcome variable will be the time to treatment failure. It will be evaluated using a Kaplan-Meier survival analysis. Secondary outcome indicators will include comparisons of FEV₁, mean peak flow variability (PM-AM peak flow difference normalized by the average of the AM and PM peak flow), methacholine airway responsiveness following premedication with salmeterol (evaluation of bronchoprotective effect), asthma symptom scores, quality of life, and rescue medication use at visits 5-11 to those obtained at visit 4.

Daily data obtained from post-randomization diary cards will be summarized and analyzed as averages. Because subjects are instructed to withhold their study salmeterol (or placebo) for 12 hours prior to a visit, the affected peak flow values will be excluded.

V. PROTOCOL

A. Subjects

1. **Sample size.** This trial has a target sample size of 150 randomized patients, with 20 in Group A, 65 in Group B, and 65 in Group C. See section X.F for the derivation of this sample size.

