In order to decrease the likelihood of incorrect drug distribution, each coded package designated for a study participant will have a sheet of removable labels attached to it. When the Clinic Coordinator retrieves a package for the study participant, he/she will remove one of the labels and attach it to the data collection form prior to mailing the form to the DCC. The Clinic Coordinator will initial across the label to indicate that he/she checked to make sure the appropriate package was distributed to the participant.

C. Randomization

When a patient at a particular center is deemed eligible for the study, the Clinic Coordinator will log into the ACRN network server and indicate to the system that a patient requires randomization. After entering the pertinent information, the Clinic Coordinator will be asked to verify that all of the information has been reviewed carefully and the patient is eligible. If so, the Clinic Coordinator will be given a packet number, from which all medication for that patient will be dispensed. In order to maintain security of the randomization schedules, the data manager of the DCC will automatically receive a notice from the ACRN network server that a patient has been randomized. If no follow-up information is forthcoming on such a patient, the data manager will contact the Clinic Coordinators concerning the status of the patient.

As described in Section IID, this protocol requires randomization of patients on two occasions. Patients at Visit 4 are randomized to either active salmeterol (13/15) or placebo salmeterol (2/15). Patients on active salmeterol at Visit 5 are randomized to receive the ICS reduction (Group C) or the sham ICS reduction (Group B), whereas the placebo salmeterol patients (Group A) will undergo the ICS reduction.

D. Stratification

The randomization scheme will be stratified according to center because differences among clinical centers typically yield a large amount of variability. In addition, each Clinical Center will be restricted to enroll no more than 25% of its target sample size of patients to be between the ages of 12 and 18.

Within subgroup I and subgroup II (see Section IID for definitions) of each clinical center an adaptive randomization scheme at Visit 5 will be invoked in order to balance the treatment arms with respect to the following strata:

ethnic group (white, black, Hispanic, native American, Asian, Other)
gender (male, female)
age (adolescent, adult)

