The strata of a particular patient are noted and the marginal frequencies of these strata are summed for each treatment arm. Then the patient is assigned to that treatment arm which has the smallest sum of marginal frequencies^[16].

E. Statistical Analysis

The primary response variables in this study are time and occurrence of treatment failure after visit 5, where treatment failure is defined in Section III. Kaplan-Meier survival curves will be constructed for the three treatment arms. Statistical tests, such as the logrank test and the generalized Wilcoxon test, will be applied to compare the survival curves of the groups.

In addition, a proportional hazards regression analysis will be applied, which allows for comparing the survival curves of the groups in the presence of other covariates. In this type of analysis the hazard function at time t is modelled as

$$h(t; \mathbf{x}) = h_0(t)\exp(\mathbf{x}^T\xi)$$

where

$h_0(t)$ is the unspecified baseline hazard,

$\mathbf{x} = [x_1 \dots x_k]^T$ is a vector of explanatory variables, and

$\xi = [\xi_1 \dots \xi_k]^T$ is a vector of unknown parameters.

The vector \mathbf{x} will include indicator variables for treatment assignment, Clinical Center, and treatment \times center interactions. The assumption of proportional hazards is important for the logrank test and the proportional hazards regression. This will be assessed via graphical procedures (comparing log survival plots) and statistical tests (including time-dependent covariates in the proportional hazards regression and testing for significance).

Safety of methacholine challenge will be examined by analyzing the frequency of adverse events following clinic visits at which methacholine challenge is performed, compared with the frequency following visits at which it is not. McNemar's test will be applied for this purpose because of the correlated responses within each subject. The efficacy of methacholine challenge will be analyzed by correlating PC_{20} with other measures of asthma outcome, such as AM and PM PEF, FEV_1 , symptom scores, rescue beta-agonist use, and quality of life scores. Correlation coefficient estimates and confidence intervals, specifically designed for longitudinal data, will be calculated for this purpose. Daily data obtained from post-randomization diary cards will be summarized and analyzed as

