Chervinsky, et al^[19] reported a 60% failure rate for a similar group of patients receiving placebo, so we assume that $\theta_A = 0.60$. Greening, et al^[8] reported a 5% failure rate for a similar group of patients receiving salmeterol and ICS, so we assume that $\theta_B = 0.05$. Although it is anticipated that $\theta_A > \theta_C > \theta_B$, there is no report in the literature as to an anticipated failure rate for Group C. As such, a rate which would be considered clinically significant was discussed at length by the ACRN Steering Committee. The committee agreed that a reduction in the treatment failure rate of Group A by more than 50% would be clearly clinically relevant in this patient population. Therefore, failure rates less than 30% were assumed for Group C in order to calculate the sample size. The Steering Committee also recognized that the eventual choice of a precise failure rate for Group C needed to reflect the relative numbers of asthmatic patients with moderate asthma within the entire asthmatic population in the United States (approximately 25% of the total) in order to set realistic recruitment goals for this disease severity category. After numerous discussions with input from various individuals, the Steering Committee agreed that a 20% treatment failure rate for Group C would be the best choice to address both the clinical

relevance of any observed differences and the patient population disease severity restraints.

It is not of interest to detect failure rates in the other direction, i.e., $\theta_B > \theta_C > \theta_A$, so one-sided tests are used. One interim analysis is planned for this trial when approximately one-half of the randomized patients have completed the trial. Therefore, a significance level of $\alpha = 0.029$ (see Pocock^[18]) will be invoked at each analysis. Using $\beta = 0.20$ (80% statistical power) and allowing for a 10% withdrawal rate, a total of 130 randomized patients are needed in Groups B and C. In order to perform the secondary comparison of Group B versus Group A, the target sample size for Group A will be 20 randomized patients. This comparison of Group C versus Group A will have 80% statistical power based on the assumed failure rates of 20% and 60%, respectively. Thus, the required sample size for this trial is 150 randomized patients.

XI. REFERENCES CITED

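### The secondary C versus A comparison is allocated by center only and modelled with no pre-salmeterol severity measure, although Visit 4 FEV1 is in hand; prespecifying it would be a cheap improvement, not the correction of an error

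*Protocol*

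**What the plan says.** Salmeterol is allocated first. Protocol X.C: "Patients at Visit 4 are randomized to either active salmeterol (13/15) or placebo salmeterol (2/15"). The only stratification that X.D attaches to this step is Clinical Center.

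Severity enters two weeks later. Section III.E defines subgroups I and II "based on severity of airway obstruction and/or PEF stability" at Visit 5. Within them, X.D says, "an adaptive randomization scheme at Visit 5 will be invoked in order to balance the treatment arms" on ethnic group, gender and age. The Visit 5 text in V.E gives Group A a sham randomization, so this balancing acts on B versus C only.

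For analysis, X.E plans Kaplan-Meier curves, logrank and generalized Wilcoxon tests, and a proportional hazards regression whose covariate vector "will include indicator variables for treatment assignment, Clinical Center" and treatment-by-center interactions. It introduces that regression as a way to compare groups in the presence of other covariates, but names no severity measure.

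The target is 150 patients, "with 20 in Group A, 65 in Group B, and 65 in Group C" (V.A). B versus C is primary. X.F calls the secondary comparison B versus A in one sentence and C versus A in the next. The power statement is for the latter: "This comparison of Group C versus Group A will have 80% statistical power based on the assumed failure rates of 20% and 60%, respectively".

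**The concern.** C versus A is the only randomized contrast that isolates salmeterol under the steroid taper. Section V.G says why Group A exists: without it, similar results in B and C could mean either that salmeterol works or that these patients needed less inhaled steroid than was thought. A chance difference in severity between 20 and 65 patients brings some of that ambiguity back.

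The Protocol treats severity as important. It selects patients on FEV1 and PEF variability, and balances B against C within subgroups built on the same two measures. The contrast with the smallest arm gets neither balancing nor a named covariate for severity, although a suitable baseline value is collected on everyone. At stake is the precision and credibility of a secondary comparison, not its validity.

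**Working it through.** **Inputs.** From X.F: failure rates of 20% (C) and 60% (A), 10% withdrawal, level 0.029 per analysis, and "so one-sided tests are used". From V.H: 50% to 60% anticipated for A. From V.A: 65 and 20 patients. Assumed, because the documents give nothing: the prognostic strength of Visit 4 FEV1, as a log hazard of 0.3, 0.5 or 0.8 per SD.

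**1. The plan's own figure.** Hazard ratio = log(1 - 0.60)/log(1 - 0.20) = 4.106, with log 1.41. Expected failures = 0.9 x (65 x 0.20 + 20 x 0.60) = 22.5. With allocation fractions 20/85 = 0.235 and 0.765, Schoenfeld power is Phi(sqrt(22.5 x 0.235 x 0.765) x 1.41 - 1.90) = 82.8%. With 19 in Group A it is 80.9%, and with 18 it is 78.8%. The stated 80% with 20 patients reproduces.

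**2. Size of chance imbalance.** The standardized baseline gap between 20 and 65 patients has SD sqrt(1/20 + 1/65) = 0.256. A gap above 0.25 SD has probability 33%, and one above 0.50 SD has probability 5%. The factor on the hazard ratio is exp(±1.96 x 0.256 x b), where b is the log hazard per SD:

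| b per SD | 95% range of the factor |
|---|---|
| 0.3 | 0.86 to 1.16 |
| 0.5 | 0.78 to 1.28 |
| 0.8 | 0.67 to 1.49 |

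For scale, the unadjusted log hazard ratio has a standard error of about 0.43. At b = 0.5 the imbalance contributes SD 0.5 x 0.256 = 0.128, and (0.128/0.43)^2 is about 9% of that variance.

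**3. Power with and without the covariate.** Simulation with 1,500 trials per setting, exponential hazards, a standard normal covariate, marginal failure rates held at the plan's values, 10% withdrawal, and a one-sided likelihood-ratio test at 0.029:

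| b per SD | A 60%, C 20%: unadjusted, adjusted | A 50%, C 20%: unadjusted, adjusted |
|---|---|---|
| 0.3 | 91.7%, 92.3% | 72.1%, 72.6% |
| 0.5 | 92.7%, 94.7% | 73.9%, 77.3% |
| 0.8 | 91.8%, 97.1% | 73.6%, 81.4% |

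The gains are 0.5 to 0.6, 2.0 to 3.4 and 5.3 to 7.8 points. Allowing for simulation error, read them as about 0 to 1, 1 to 4 and 5 to 8.

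A second simulation (4,000 trials per setting, 60% versus 20%) agrees. At hazard ratios of 1.25, 1.5 and 2.0 per SD, power goes from 89.7% to 89.7%, 90.0% to 92.0% and 91.5% to 95.6%. Neither simulation modelled centers. Repeating the comparison within six center strata left the covariate's gain in much the same range. Stratifying itself cost a few points at most when centers truly do not differ.

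**4. What adjustment costs.** In the second simulation the standard error of the log hazard ratio rises from 0.431 to 0.441 at 1.5 per SD, and from 0.430 to 0.447 at 2.0. The target also changes: a marginal hazard ratio of 4.11 corresponds to a conditional 4.35 at 1.5 and 4.89 at 2.0. Any power gain comes from that larger conditional effect, not from a smaller standard error. Type I error was 2.6% to 3.2% adjusted and 2.3% to 3.0% unadjusted, against a nominal 2.9%.

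**5. Parameters.** V.B names six centers. For C versus A, treatment (1), center (5) and interaction (5) use 11 parameters on about 22 failures, with about 20/6 = 3.3 Group A patients per center.

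**The case against.** The strongest reply is that nothing in X.E is false. Saying which terms the vector will include does not exclude others, X.E itself mentions other covariates, and a statistical analysis plan that is not shown may name them. That stands, and it is why this is an improvement and not an error. It does not dispose of the point: X.E does name its terms, and for C versus A the named set spends 11 parameters on center and interaction and none on severity.

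Stronger readings are tempting, and the documents do not support them:

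- *That the unadjusted comparison is biased.* Under randomization, chance imbalance is ordinary sampling error. The unadjusted test held its level in simulation.
- *That adjustment adds power at no cost and removes chance imbalance.* The gain needs a prognostic strength the documents do not give, and is nil at a hazard ratio of about 1.25 per SD or below. The standard error rises and the hazard ratio becomes conditional. Only the modelled covariate is corrected, and only if its form is right.
- *That the plan will adjust contrasts with Group A for the Visit 5 subgroup.* That subgroup is measured after two weeks of randomized treatment, so conditioning on it would be wrong. But the Protocol Overview classifies only Group B/C patients, and no section uses the subgroup for Group A.

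It can also be said that Visit 4 FEV1 is an imperfect severity score here. Patients above 80% predicted enter because of PEF variability, and the in-clinic failure criteria in III.F are relative to the patient's own Visit 4 FEV1. A linear term may therefore predict failure weakly. That stands, and calls for a sensitivity analysis.

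**Conclusion.** The point holds as a modest improvement to a secondary comparison. The documents establish that the A allocation is stratified by center only, that Visit 5 balancing cannot reach Group A, and that the named model has no pre-salmeterol severity term although one is collected. The planned unadjusted test is valid, and its power at the plan's rates reproduces (82.8% against the stated 80%).

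The benefit of adjusting is conditional: from almost nothing to about 8 points of power over the assumed range, plus correction for chance imbalance in one variable. It is most useful if Group A fails at the low end of its anticipated range, where simulated unadjusted power is about 72% to 74%. The conclusion rests on the assumed prognostic strength, a roughly linear effect of FEV1 and proportional hazards. The primary B versus C comparison is not affected.

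**What to change.** In X.E, prespecify for C versus A a Cox model stratified by Clinical Center, with treatment and continuous Visit 4 prebronchodilator FEV1 (% predicted) as its only terms. Leave treatment-by-center interactions out of this comparison: about 22 expected failures cannot support them. Keep center in the analysis, because it is the one factor on which the Visit 4 randomization is stratified. Report the unadjusted logrank test alongside. Add PEF variability from weeks 5 and 6 as a covariate in a sensitivity analysis, since it is the other route into the trial. In X.F, make the name of the secondary comparison consistent.

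The cost is wording only, using data already collected, with one extra parameter. The price in the analysis is a slightly larger standard error and a conditional instead of a marginal hazard ratio, which the report should state.

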5. Is there a difference in the frequency of asthma exacerbations following clinic visits at which methacholine challenge is performed, compared with visits at which it is not?
6. How does PC_{20} compare with other measures of asthma outcome, such as AM and PM PEF, FEV₁, symptom scores, rescue beta-agonist use, and quality of life scores?

L. Protocol Overview

[figure not shown]
Mch = Methacholine responsiveness
 S = Spirometry
 QOL = Quality of life questionnaire

R = Reversibility with bronchodilator
 SI = Sputum induction/analysis
 DR = Diary Review

SLIC PROTOCOL

Group A = OFF Salmeterol; ICS reduction
 Group B = ON Salmeterol; no ICS reduction
 Group C = ON Salmeterol; ICS reduction

GROUPS

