Since inhaled corticosteroid therapy will be first reduced and then eliminated in 2 of the 3 study populations, it is anticipated that asthma exacerbations will occur. The protocol contains a number of "safety nets" including frequent visits, phone calls, and well described rescue algorithms so that exacerbation can be recognized early and appropriately treated by both the patient and the ACRN medical support staff. Once an exacerbation requiring oral or parenteral corticosteroid treatment has occurred, the patient will be placed back on their initial dose of inhaled corticosteroid and continued to be followed per the visit schedule designated in the protocol. This event will be recorded as a significant asthma exacerbation rather than an adverse event. Information and data gained as a result of these subsequent visits will be utilized in the "intent to treat" analysis. Should asthma exacerbations become too frequent or too severe following randomization, the ACRN principal investigator may elect to drop the patient from further study participation. Study termination procedures will be completed. Any complication resulting from an asthma exacerbation (pneumothorax, pneumomediastinum, mechanical ventilation, etc.) will be recorded as an adverse event in addition to the documentation also recorded for the significant asthma exacerbation. (See SOCS/SLIC MOP for further details regarding early study termination).

2. Other Medical Complications from Therapy

Complications from chronic salmeterol therapy have been reported to occur in about 12% of patients compared to 23% in patients receiving scheduled albuterol, and 20% of patients only receiving albuterol on a PRN basis^[4].

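### The methacholine safety analysis counts adverse events, which by rule exclude steroid-treated exacerbations, and an unadjusted McNemar test cannot separate methacholine from treatment changes made only at methacholine visits

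*Protocol*

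**What the plan says.** Section II.C, question 5, asks: "Is there a difference in the frequency of asthma exacerbations following clinic visits at which methacholine challenge is performed", compared with visits without it. Section X.E plans to answer by "analyzing the frequency of adverse events following clinic visits at which methacholine challenge is performed", against the frequency after the other visits, and adds: "McNemar's test will be applied for this purpose because of the correlated responses within each subject". It gives no time window and no rule for turning several visits of each kind into one pair per patient.

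Section VII.B.1 sets the recording rule. It applies "Once an exacerbation requiring oral or parenteral corticosteroid treatment has occurred", and then: "This event will be recorded as a significant asthma exacerbation rather than an adverse event". Only complications of an exacerbation, such as a pneumothorax, "will be recorded as an adverse event in addition to the documentation also recorded for the significant asthma exacerbation".

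The visit schedule (Sections V.E and V.F) places methacholine challenge at visits 1, 4, 5, 6, 7, 9 and 11. Visits 2, 3, 8 and 10 and the drug-swap visits at weeks 10 and 14 have none. Blinded salmeterol or placebo starts at visit 4. The ICS reductions are at visits 5 and 7 (Section III.G), real in Groups A and C and sham in Group B.

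**The concern.** The question and the analysis name different outcomes, and a third section removes from the analysed outcome a class of events that the question is about. The removal goes by severity: an exacerbation treated without oral or parenteral corticosteroid can still meet the broad adverse-event definition in Section VII.A, while one that needed such treatment is recorded elsewhere. A comparison showing no excess after methacholine would then say little about the exacerbations that matter most.

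The second problem lies in the schedule. Each planned change of blinded treatment takes effect at a methacholine visit and none at a visit without methacholine. If exacerbations are counted, as question 5 intends, an unadjusted within-patient comparison contrasts methacholine plus treatment change with neither. Methacholine safety is a stated purpose of the study (Section II.B), so the answer should be interpretable.

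**Working it through.** X.E states no event rate, significance level or power for this comparison, so there is no figure to reproduce.

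**Outcome.** Question 5: exacerbations. X.E: adverse events. VII.B.1: exacerbations needing oral or parenteral corticosteroid are not adverse events. The three cannot all be followed. For scale, the failure rates and group sizes assumed in Section X.F give 0.60 × 20 + 0.05 × 65 + 0.20 × 65 = 12 + 3.25 + 13 = 28.25 treatment failures. Those treated with oral or parenteral corticosteroid would not be counted under X.E; the protocol does not say what share that is.

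**Treatment changes.** Visit 4 (all 150 patients), visit 5 and visit 7 (Groups A and C: 20 + 65 = 85 of 150) are all methacholine visits. McNemar's test has no covariate with which to adjust.

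**Visit sets.** Windows run from one clinic visit to the next; visit 11 has no scheduled follow-up.

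- Methacholine: weeks 0–2, 6–8, 8–10, 12–14, 16–18, 20–22 (six).
- None: weeks 2–4, 4–6, 10–12, 14–16, 18–20, 22–24 (six).
- After randomisation: five v four. If swap visits are ignored and windows run to the next numbered visit, methacholine has 2 + 4 + 4 + 2 + 2 = 14 weeks against 2 + 2 = 4 weeks.

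Assume no methacholine effect, the same risk p in every two-week window, independent windows, n = 150, two-sided 5% and no continuity correction. With m and k windows, P = 1 − (1 − p)^m and Q = 1 − (1 − p)^k. The expected discordant counts are b = nP(1 − Q) and c = nQ(1 − P). The test rejects when (b − c)²/(b + c) exceeds 3.84, and the rejection probability is summed over the distribution of discordant pairs. At p = 2%:

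| Counting | m v k | Any event | b v c | Rejects |
|---|---|---|---|---|
| Whole trial, swap visits counted | 6 v 6 | 11.4% v 11.4% | 15.2 v 15.2 | 5% |
| After randomisation, swap visits counted | 5 v 4 | 9.6% v 7.8% | 13.3 v 10.5 | 9% |
| After randomisation, numbered visits, equal two-week windows | 5 v 2 | 9.6% v 4.0% | 13.8 v 5.4 | 51% |
| Same, windows to next numbered visit | 7 v 2 | 13.2% v 4.0% | 19.0 v 5.2 | 85% |

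At p = 1%, 5% and 10%, five v four gives 6%, 14% and 22%; the last row gives 53%, 99% and 100%.

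The 2% is an assumption. Spreading 28.25/150 = 18.8% over the nine two-week periods of weeks 6–24 gives 1 − (1 − 0.188)^(1/9) = 2.3%. Significant exacerbations are a subset of treatment failures (Section VI.A), so 2% is towards the upper end for them.

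**Equal sets do not remove the confounding.** Set visits 5 and 7 against visits 8 and 10, with p = 5% and the ICS step multiplying risk by an assumed 1.5, 2 or 3 in 85 of 150 patients. The test rejects in 12%, 28% and 71% of trials (7% to 94% over p = 2% to 10%). None of these multipliers is in the protocol.

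**The case against.** Three arguments have weight.

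First, Section VII.B lists exacerbations under a heading for potential clinical adverse events, only steroid-treated ones are excluded, and Section VI.F records exacerbation measures as outcomes. It is true that no data are lost and that the exclusion is partial. But the specific recording rule beneath the heading governs, and X.E names adverse events.

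Second, a reader might infer from the unequal visit sets that the planned test would falsely indict methacholine in about 85% of trials. The documents do not support that. X.E speaks of clinic visits, and patients do return to the centre at weeks 10 and 14. No adverse-event assessment is scheduled at those two visits, but this does not disqualify them: what matters is events afterwards, which are picked up at visits 6 and 7 on forms that carry dates (Section VII.C). Pairing and window may properly be left to an analysis plan, and valid pairs exist. One qualification: a significant run-in exacerbation removes the patient (Section VI.A), so for exacerbations in randomised patients the balanced six v six count reduces to five v four.

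Third, a reader might infer that the ICS reductions must bias the result against methacholine. With swap visits counted, Groups A and C spend four weeks in each set at the first reduced dose and four weeks in each at zero. Bias then needs the risk just after a step to differ from the risk later, which the protocol does not state. On the narrow count, both comparison windows (after visits 8 and 10) are at zero ICS in Groups A and C, which could push the other way. So direction and size are open. What remains is that the changes and methacholine coincide by design and the named test cannot adjust for it.

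**Conclusion.** The point holds in a limited form and at moderate severity. The outcome contradiction between II.C, VII.B.1 and X.E is fixed by the text and does not depend on any assumption. The alignment of all three treatment changes with methacholine visits is likewise fixed by the schedule, but how far and in which direction it would distort the comparison cannot be derived from the protocol. The false-positive rate from unequal visit sets is not a property of the plan as written. Under an assumed 2% risk per two weeks it runs from nominal through about 9% to 51–85%, and the upper range arises only when run-in and swap visits are left out. The absence of a pairing rule is not itself the error.

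This is one of two additional questions in Section II.C. The primary comparison of Groups B and C and the sample size are untouched.

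**What to change.** In X.E, name significant asthma exacerbation (as defined in Section VI) as the outcome for question 5, with adverse events secondary. Score every post-randomisation clinic visit with follow-up, drug-swap visits included, for an event within one equal window. Then choose one of two analyses:

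- A visit-level model, conditional on patient or clustered by patient, with a term for a treatment change at that visit: the visit 4 start, and the ICS step at visits 5 and 7 where it is real.
- McNemar's test restricted to matched visits with the same window and no treatment change at either, for example visit 9 against visit 10.

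Group B, whose reductions are sham, can serve only as a supportive check: 0.05 × 65 = 3.25 treatment failures are expected there.

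The change rewrites one paragraph and uses data already collected. It costs slightly more programming and some precision, because visits with a treatment change then add little to the methacholine contrast.
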